A total of 34 germinal vesicle (GV) stage oocytes exhibiting normal morphology were retrieved via the ovum pick-up (OPU) procedure from 15 women diagnosed with PCOS undergoing IVF treatment at Permata Hati Infertility Clinic between 2023 and 2024. An initial pilot experiment tested three different concentrations of PRP supplementation (5%, 25%, and 50%) using three GV-stage oocytes per group. The concentration that provided the highest maturation rate while maintaining the quality and stability of the culture medium was selected as optimal.

Following this, the remaining 28 GV-stage oocytes were randomly allocated into two groups: a control group receiving no PRP (0%, n=14) and a treatment group supplemented with PRP at the optimal concentration (5%, n=14). Prior to evaluation, cumulus-oocyte complexes (COCs) were enzymatically denuded with hyaluronidase (Vitrolife, Sweden) and mechanically cleaned using micropipettes (170 μ m and 140 μ m) to remove cumulus cells, enabling direct assessment of PRP effects on oocytes. Each oocyte was then cultured for 24 hours at 37°C in either control media (G-IVF™) or treatment media containing PRP at one of the three tested concentrations.

The primary outcome was oocyte maturation, defined by the transition from GV to MII stage, determined by the presence of the first polar body after 24 hours. Secondary outcomes included total oocyte score (TOS) and fertilization outcomes. TOS is a semi-quantitative morphological assessment of oocyte quality, based on six parameters: oocyte shape, size, ooplasm characteristics, perivitelline space, zona pellucida thickness, and polar body morphology. Each parameter was scored on a standardized three-point scale (+1, 0, -1) according to the system by Lazzaroni-Tealdi [14]. Raw TOS data and scoring criteria are available in Mendeley Data. Fertilization was evaluated approximately 17 \pm 1 hours post-injection, consistent with standard pronuclear assessment for ICSI-derived zygotes, with fertilization defined by the presence of two pronuclei (2PN) and two polar bodies under microscopy.

PRP and Culture Media Preparation

To reduce confounding factors, allogenic PRP was utilized. A healthy female donor aged 20–30 years, with a history of spontaneous pregnancy and no reproductive disorders, was selected. Blood (35 mL) was collected and centrifuged sequentially at 103 \times g for 10 minutes and 230 \times g for 15 minutes, yielding approximately 12 mL of PRP, which was aliquoted into 1.5 mL microtubes and stored at -80°C until use. PRP preparation followed routine clinical procedures; however, details such as platelet and leukocyte counts or growth factor quantification were not recorded.

Oocyte maturation was conducted in G-IVF PLUS medium (Vitrolife, Gothenburg, Sweden). PRP stock solutions were prepared at 5%, 25%, and 50% concentrations. Frozen aliquots were thawed at room temperature for 10 minutes prior to mixing with the culture medium, and remaining stocks were kept frozen until required.

Statistical Analysis

Maturation outcomes were analyzed using Fisher's exact test in IBM SPSS Statistics version 25 (IBM Corp., Armonk, NY, USA), with statistical significance defined as $p < 0.05$. This method

was chosen due to the small sample size and comparable variance among groups. Because of unequal MII oocyte counts across groups, TOS analysis was not performed statistically to avoid bias from sample size imbalance; TOS results are presented descriptively.

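### 5% PRP is labelled optimal after a pilot of three oocytes per concentration, too few to rank concentrations on maturation unless true differences are large; the oocyte counts also conflict

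*Combined protocol and SAP*

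**What the plan says.** All of this is in the opening section of the combined protocol and SAP (design, groups and outcomes; no heading shown).

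- Pilot: "An initial pilot experiment tested three different concentrations of PRP supplementation (5%, 25%, and 50%) using three GV-stage oocytes per group".
- Selection rule: "The concentration that provided the highest maturation rate while maintaining the quality and stability of the culture medium was selected as optimal". It combines maturation with a criterion on the medium. No tie rule, required margin or reason for three per group is given.
- The label is repeated for the main experiment, which has an untreated arm of 14 and "a treatment group supplemented with PRP at the optimal concentration (5%, n=14". Neither 25% nor 50% is carried forward.
- Maturation is also the trial's main endpoint: "The primary outcome was oocyte maturation, defined by the transition from GV to MII stage".
- Counts: "A total of 34 germinal vesicle (GV) stage oocytes exhibiting normal morphology were retrieved", and after the pilot "the remaining 28 GV-stage oocytes were randomly allocated into two groups".

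Under Statistical Analysis, "Maturation outcomes were analyzed using Fisher's exact test in IBM SPSS Statistics version 25". Nothing there bears on the choice between concentrations.

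**The concern.** *Optimal* asserts a ranking: 5% is the best of the three. The first criterion in the rule is the maturation rate, which is also the primary outcome, so a reader is likely to take the label as a finding that 5% matures oocytes better than 25% or 50%. With three oocytes per arm the observed rate can only be 0, 1/3, 2/3 or 1. Ties for the top are common, and an inferior concentration can easily come out ahead. The main experiment has no second PRP concentration, so it cannot repair this.

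The counts matter for a different reason. The 5% v 0% comparison is untouched by the dose selection only if the pilot oocytes are separate from the 28. The word *remaining* implies that they are, but the numbers do not bear it out.

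**Working it through.** **Inputs from the opening section.** Three concentrations, n = 3 each, binary maturation outcome; 34 oocytes in total; 28 in the main experiment (14 + 14). There is no pilot operating characteristic in the documents to reproduce.

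**Assumptions.** True maturation rates are not given, so a range is used. Oocytes are treated as independent, although they came from 15 women. Selection is on maturation alone, with ties split at random; by chance alone the best is picked 1/3 of the time.

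**Formula.** Let the best concentration have rate p and the other two both have rate q. Write a_i = C(3,i) p^i (1−p)^(3−i), define b_i in the same way with q, and let c_i = b_0 + … + b_(i−1). Then

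P(pick best) = Σ a_i (c_i² + c_i b_i + b_i²/3), i = 0 to 3.

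The three terms cover both rivals below, one rival tied, and both tied.

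- 70/50/50%: 0.0001 + 0.0207 + 0.2136 + 0.3019 = 0.536.
- 80/40/40%: 0.0001 + 0.0194 + 0.2435 + 0.4799 = 0.743.

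Full enumeration of the 64 outcomes gives the same values and handles unequal rivals:

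| True rates (%) | P(pick best), n = 3 |
|---|---|
| 70/50/50 | 0.536 |
| 70/50/30 | 0.623 |
| 80/40/40 | 0.743 |
| 70/30/10 | 0.815 |
| 80/40/10 | 0.832 |
| 80/30/10 | 0.885 |

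**Lead needed for 80% correct selection, rivals equal**

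| Both rivals at | Best must be at | Lead (points) |
|---|---|---|
| 0% | 33.1% | 33 |
| 5% | 43.3% | 38 |
| 10% | 52.0% | 42 |
| 20% | 65.9% | 46 |
| 30% | 76.7% | 47 |
| 40% | 85.7% | 46 |
| 50% | 93.2% | 43 |

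The 0% row has a closed form: P = 1 − (2/3)(1−p)³ = 0.80 gives (1−p)³ = 0.30, so p = 0.331. With unequal rivals, a 40-point lead over the runner-up is enough in the 70/30/10% and 80/40/10% rows of the first table.

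The smallest n per concentration for 80% correct selection is 17 at 70/50/50%, 10 at 70/50/30% and 5 at 80/40/40%.

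**Precision of a single arm.** Exact 95% intervals: 0/3 is 0–71%, 1/3 is 1–91%, 2/3 is 9–99%, 3/3 is 29–100%.

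**Counts.** 3 × 3 = 9 in the pilot; 9 + 28 = 37, against 34 stated; 34 − 9 = 25, against 28 stated; 34 − 28 = 6, against 9 stated.

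One arrangement that gives 34 is for the three 5% pilot oocytes to sit among the 14 treated: 6 others + 28 = 34. If that had happened and PRP had no effect at a common rate p, the treated rate would be inflated on average by (E[max of three Binomial(3,p)] − 3p)/14:

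- p = 0.3: (1.557 − 0.9)/14 = 0.047
- p = 0.5: (2.203 − 1.5)/14 = 0.050
- p = 0.7: (2.706 − 2.1)/14 = 0.043

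**The case against.** The best defence is that *optimal* is defined where it is used: it names whatever the joint rule selects, and the second use refers back to the first. The text does not say that 5% is best on maturation alone, and a pilot that picks a working dose needs no significance test. This stands as a defence of the rule and of using 5%. It does not rescue the label, because the text does not say which criterion excluded 25% and 50%, and highest maturation rate is half of the definition.

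It is also fair that the probabilities above model only half the rule. The medium criterion could remove arms or break ties, so they are not the chance that the full procedure chooses correctly. They show how much information the pilot carries about maturation. If the medium decided the matter, the label says nothing about maturation at all.

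A particular pilot result could be informative. A 3/0/0 split gives a three-group exact p of 3/84 = 0.036 and, with uniform priors, about 97% posterior probability that the 3/3 arm is best. But a 3/0/0 split in favour of the true best has probability only 0.005 at 70/50/50%, 0.024 at 80/40/40% and 0.128 at 80/30/10%. Even then 3/3 v 0/3 gives a two-sided Fisher p of 0.10.

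Readers might draw four stronger conclusions that the documents do not support:

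- *A lead of 42–47 points is always required.* That holds for equal rivals at 10–50%; less is enough when the rivals are near zero or unequal.
- *5% is a bad dose, or the 5% v 0% comparison is invalid.* Weak dose selection does not bias a later comparison in separate oocytes.
- *Pilot oocytes were reused.* This is one way to reach 34, not a stated fact; a typing error in any of the three counts would explain the conflict equally well.
- *The pilot results were withheld.* Only methods text is visible, so absent counts are no evidence of that.

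**Conclusion.** The concern holds in limited form, and its severity is minor. Three oocytes per concentration cannot reliably show which concentration is best for maturation unless the true lead is large: about 42–47 points with rivals equal at 10–50%, and roughly 33–40 points with rivals near zero or unequal, for 80% correct selection. At a 20-point lead (70/50/50%) the choice is right little more than half the time. These figures rest on assumed rates, independent oocytes and selection on maturation alone. The conclusion that the main experiment cannot support optimality among concentrations needs no assumption, since it contains only 0% and 5%.

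The count conflict is a separate error and is certain as arithmetic: 37 against 34. Its cause is unknown. Reuse of the pilot's 5% oocytes, if it occurred, would add about 4–5 points to the treated rate under no effect (true rate 30–70%). That is conditional and does not raise the severity of the labelling point.

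**What to change.** 1. In both places in the opening section, replace *optimal* with: the concentration carried forward from a feasibility pilot (on maturation and medium stability).
2. Draw no conclusion that 5% matures oocytes better than 25% or 50%. If medium quality or stability is what excluded the higher concentrations, say so; a conclusion on that ground may stand.
3. Correct whichever of the three counts is wrong (34 in total, 9 in the pilot, 28 in the main experiment) so that they add up, and state whether any pilot oocyte is among the 28. If any is, exclude it from the 5% v 0% comparison.

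It would help to give the pilot counts by concentration with exact intervals beside the finding on the medium, but their absence from methods text is missing detail rather than an error.

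The cost is two wording changes and a sentence or two on counts; no new oocytes are needed. The claim about 5% becomes weaker. If all three 5% pilot oocytes had been reused, the treated group would fall from 14 to 11 and the analysed total from 28 to 25; otherwise the analysis need not change.

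### The oocyte counts do not reconcile: 34 less a 9-oocyte pilot leaves 25, not the 28 said to be randomised, and the plan must say whether any pilot oocyte is in the PRP arm

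*Combined protocol and SAP*

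**What the plan says.** All the counts stand in the unnumbered opening section of the combined protocol and SAP.

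- Total: "A total of 34 germinal vesicle (GV) stage oocytes exhibiting normal morphology were retrieved".
- Pilot: the first experiment "tested three different concentrations of PRP supplementation (5%, 25%, and 50%) using three GV-stage oocytes per group". No 0% pilot group is described, and nothing is said about how the pilot oocytes were assigned.
- Choice of concentration: "The concentration that provided the highest maturation rate while maintaining the quality and stability of the culture medium was selected as optimal".
- Main experiment: "the remaining 28 GV-stage oocytes were randomly allocated into two groups". The arms are "a control group receiving no PRP (0%, n=14") and "a treatment group supplemented with PRP at the optimal concentration (5%, n=14").

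The primary outcome is maturation from GV to MII at 24 hours, so the pilot's main selection criterion is also the primary outcome. The Statistical Analysis section tests it with Fisher's exact test at p < 0.05 and does not state sidedness. Neither section reports exclusions, mentions pooling or reuse of pilot oocytes, or explains how 28 was reached.

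**The concern.** Taken as two separate sets of oocytes, the pilot and the main experiment use three more than were collected. Three is also the size of one pilot group, which raises the question of whether the 5% pilot oocytes were counted again in the 5% arm.

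Two things are at stake. The first is the sample size: a reader cannot tell which of the total, the pilot group size or the number randomised is right. The second arises only if pilot oocytes were reused. Then 3 of the 14 PRP oocytes (21%) would lie outside the randomisation that the plan describes and would have been cultured before it. Their outcomes would have helped to choose 5% and would then count as evidence for 5%. The Fisher test would no longer be a test on 28 randomised oocytes.

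**Working it through.** **Inputs from the opening section:** total 34; pilot groups 3; oocytes per pilot group 3; number randomised 28; arms 14 and 14.

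**1. Reproducing the plan's figure**

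- Pilot oocytes: 3 x 3 = 9.
- Left after the pilot: 34 - 9 = 25. The plan's 28 is not reproduced.
- Total needed if the phases are separate: 9 + 28 = 37, against 34 printed.
- Gap: 37 - 34 = 3.
- The arms do sum to the stated number: 14 + 14 = 28.

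Exclusions would not close the gap, because they would lower the number remaining, not raise it.

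**2. What would reconcile the counts**

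| Explanation | Check |
|---|---|
| Total misprinted | 9 + 28 = 37 |
| Number randomised misprinted | 34 - 9 = 25 |
| Pilot group size misprinted | (34 - 28) / 3 = 2 per group |
| No misprint; 5% pilot group counted in the PRP arm | 14 (0%) + 14 (5%) + 3 (25%) + 3 (50%) = 34 |

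If every printed number is kept, the overlap must be the 5% group, because oocytes cultured at 25% or 50% cannot belong to arms of 0% and 5%. Assuming an undocumented 0% pilot group of three does not change this. The total is then 34 only if both the 0% and the 5% pilot groups are carried over (28 + 3 + 3 = 34).

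**3. Effect of reuse, if it occurred**

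The documents give no maturation rate, so I assume a true rate p of 0.3 to 0.7, the same at every concentration (no PRP effect). The pilot group with the highest rate is selected, with ties broken at random. The PRP arm is then the maximum of three Bin(3, p) counts plus Bin(11, p), and control is Bin(14, p). Fisher's test is taken as two-sided at 0.05, and the calculation is by exact enumeration.

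The gain in the PRP arm rate is 3 x (expected rate of selected pilot group - p) / 14.

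| p | Expected rate, selected pilot group | Gain in PRP arm | False positives favouring PRP: clean 14 v 14, then reuse | Total two-sided error: clean 14 v 14, then reuse |
|---|---|---|---|---|
| 0.3 | 0.519 | 0.047 | 0.0106, 0.0182 | 0.0211, 0.0219 |
| 0.4 | 0.633 | 0.050 | 0.0099, 0.0167 | 0.0198, 0.0199 |
| 0.5 | 0.734 | 0.050 | 0.0087, 0.0154 | 0.0174, 0.0188 |
| 0.6 | 0.825 | 0.048 | 0.0099, 0.0181 | 0.0198, 0.0226 |
| 0.7 | 0.902 | 0.043 | 0.0106, 0.0184 | 0.0211, 0.0230 |

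For example, at p = 0.5: 3 x (0.734 - 0.5) / 14 = 0.050. The total hardly changes because false results against PRP fall, from about 0.009-0.011 to about 0.003-0.005.

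**4. Effect on a single result**

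These tables are invented, since the documents give no outcome data. In each, three matured pilot oocytes are removed from the PRP arm.

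| PRP v control, with pilot oocytes | p | Without them | p |
|---|---|---|---|
| 12/14 v 6/14 | 0.046 | 9/11 v 6/14 | 0.099 |
| 12/14 v 5/14 | 0.018 | 9/11 v 5/14 | 0.042 |
| 13/14 v 6/14 | 0.013 | 10/11 v 6/14 | 0.033 |
| 13/14 v 7/14 | 0.033 | 10/11 v 7/14 | 0.042 |

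Only the first crosses 0.05.

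**The case against.** A reader might infer that the 5% pilot oocytes were in fact put into the PRP arm, because that allocation alone keeps every printed number. The documents do not support this as a finding. It saves the numbers at the expense of the words: pilot oocytes that had already been cultured were neither left over after the pilot nor part of the random allocation described. One misprint resolves the section just as simply, and two oocytes per pilot group gives 28 exactly. The match 34 - 6 = 28 therefore does not single out reuse.

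A reader might also infer that the 14 v 14 denominators are wrong. That is not shown. If the error lies in the total or in the pilot group size, 14 v 14 is correct and fully randomised. Nor is it established that the pilot oocytes were not randomised, since the text is silent on how they were assigned.

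On size, the rise in PRP-favouring errors should not be quoted alone. Total two-sided error stays below half of the nominal 5% even with reuse, because Fisher's test is conservative at these numbers. The calculation also ignores the second selection criterion, medium quality and stability. If a concentration was ruled out on that ground, the selection bias is smaller.

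All of this stands, and it limits the point to a conditional one. It does not remove the contradiction in the counts: nothing else in the documents resolves it, and no redaction or broken table accounts for it.

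**Conclusion.** The contradiction is certain: 34, a pilot of nine and 28 left to randomise cannot all be true of separate oocytes. At least one figure is wrong, or the three 5% pilot oocytes are counted in the PRP arm. The documents do not allow a choice between these explanations. Because the number randomised is the sample size of the primary comparison, the counts must be corrected whichever holds.

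Reuse is an open question for the investigators. If it occurred, the comparison would no longer be purely randomised, and that is the firmer part of the harm. The selection bias would be modest on average: about 4-5 points on the PRP arm rate, and PRP-favouring false positives of about 1.5-1.8% in place of 0.9-1.1%, with total two-sided error of about 1.9-2.3% in place of 1.7-2.1%. These figures assume no true effect, maturation of 30-70%, a two-sided test and selection on maturation alone, and should be read as an upper case. A borderline result could still change sides of 0.05.

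**What to change.** 1. Reconcile the total, the pilot group sizes and the number randomised against the laboratory log, and correct whichever figure is wrong.
2. Give an oocyte flow by concentration (0%, 5%, 25%, 50%) and by phase (pilot, main).
3. State plainly whether any pilot oocyte is included in the 14 of the PRP arm.
4. Only if the answer is yes: restrict the primary Fisher test to oocytes randomised after the concentration was chosen (14 - 3 = 11 PRP v 14 control), report the pilot oocytes separately, and label any pooled result a non-randomised sensitivity analysis.

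The cost of steps 1 to 3 is a log check and a few lines of text. Step 4 adds one re-run of a 2x2 test. Its downside is three fewer PRP oocytes and probably a larger p-value, which in a borderline table could pass 0.05. If no pilot oocyte was reused, the 14 v 14 analysis can stand once the log confirms those numbers.

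### No split by woman or retrieval day is reported for the 28 randomised oocytes, which may leave avoidable between-woman noise in the PRP comparison

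*Combined protocol and SAP*

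**What the plan says.** The opening (unnumbered) methods section gives the source: "A total of 34 germinal vesicle (GV) stage oocytes exhibiting normal morphology were retrieved via the ovum pick-up (OPU) procedure from 15 women", collected over 2023–2024. A pilot tested three PRP concentrations "using three GV-stage oocytes per group". After that, "the remaining 28 GV-stage oocytes were randomly allocated into two groups": 14 without PRP and 14 at 5%. The unit allocated is the oocyte. The section mentions no stratum, block or list, and does not say how the draw was made as oocytes arrived over time. It does not give oocytes per woman, women per arm, or how many women contributed to both arms.

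The Statistical Analysis section compares maturation between arms with Fisher's exact test and describes no term for woman or retrieval day.

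**The concern.** Oocytes from one woman share her biology and, where retrieved together, the retrieval day. If their chances of maturing are correlated, an arm that happens to draw more oocytes from favourable women looks better for reasons unrelated to PRP. Sending each woman's oocytes to both arms cancels most of this by design and uses no extra material. With only 14 oocytes per arm, precision is scarce, so a gain that costs almost nothing is worth taking.

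**Working it through.** **Inputs from the document:** 34 oocytes, 15 women, pilot of 3 × 3 = 9, then 28 allocated 14 v 14; binary primary outcome; Fisher's exact test at 0.05.

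**Assumptions (not in the document):** ICC ρ from 0 to 0.5; 50% maturation for the variance calculation; all 15 women contribute to the 28; three possible layouts of oocytes per woman:
- A: 13 women × 2 and 2 women × 1
- B: 5, 4, 3, four women × 2, eight women × 1
- C: one woman × 14 and 14 women × 1 (extreme)

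**Step 1, the document's own count.** 34 − 9 = 25, not 28, and 28 + 9 = 37, not 34. The figure 28 equals 34 − 6. One arithmetic reconciliation is 14 + 14 + 3 + 3 = 34, which would place the three 5% pilot oocytes inside the treatment group. The document does not say this. The steps below take 28 as stated.

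**Step 2, siblings must exist.** 28 − 15 = 13 oocytes beyond one per woman. The mean is 28/15 = 1.87, so some women supply only one. Under an unrestricted 14:14 draw, a given sibling pair is split with probability 14/27 = 52% and lands in one arm with probability 13/27 = 48%. In layout A about 13 × 13/27 = 6.3 of the 13 pairs are not split.

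**Step 3, variance.** Code arm as z = ±1. Then

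Var(RD) = [p(1 − p)/196] × V, with V = (1 − ρ) × 28 + ρ × Q,

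where Q sums the expected squared total of z within each woman. For a woman with m oocytes the contribution is m(28 − m)/27 under an unrestricted draw. Under a within-woman split it is 0 if m is even and 1 if m is odd.

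| Layout | Q unrestricted | Q split | Ratio, ρ = 0.1 | ρ = 0.3 | ρ = 0.5 |
|---|---|---|---|---|---|
| A | 27.04 | 2 | 1.10 | 1.37 | 1.83 |
| B | 26.30 | 10 | 1.06 | 1.22 | 1.43 |
| C | 21.26 | 14 | 1.03 | 1.09 | 1.17 |

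Example, layout A at ρ = 0.3: unrestricted V = 19.6 + 0.3 × 27.04 = 27.7; split V = 19.6 + 0.3 × 2 = 20.2; ratio 1.37. At ρ = 0 every ratio is 1.

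**Step 4, on the risk-difference scale.** With p = 0.5, SD = √(0.25 V/196). At ρ = 0.3, unrestricted to split:
- A: 18.8 to 16.1 points
- B: 18.7 to 17.0 points
- C: 18.2 to 17.4 points

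In oocytes, 28 × 1.09 = 30.5 and 28 × 1.37 = 38.4, so the split is worth about 3 to 10 extra oocytes at this ICC.

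**Step 5, power and type I error (simulation, error about 1 point).** The illustrative rates are assumptions.
- 40% v 80%, mid-p, layouts A and B, latent within-woman correlation 0.3–0.7 (outcome ICC about 0.2–0.5): about 0.53–0.56 for an unrestricted draw, against 0.57–0.67 for a split tested by re-randomisation in the same strata. Type I error with the split was at or below about 5%.
- At zero correlation the split costs up to about 1–2 points of mid-p power, or about 5 points without mid-p.
- 30% v 80%, split but Fisher kept (layout A and another mixed layout): 0.65–0.67 against 0.65–0.66 for the unrestricted draw, so essentially no gain. Fisher also becomes more conservative.
- 30% v 80%, split with a strictly within-woman exact test: 0.49–0.67, so power may fall, because single oocytes and women whose oocytes all have the same result carry no information.
- Type I error of Fisher under the unrestricted draw: 0.012–0.023, so no inflation.

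**The case against.** Several stronger readings are tempting, and the document does not support them.

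- *The oocytes were drawn as one pool, ignoring the woman.* The text is silent; it says only that allocation was random. What can be said is that no restriction is reported. The unrestricted figures above describe that reading.
- *The PRP effect is confounded.* Under true randomisation, differences between women and dates are random error already within the sampling variance, and the simulated type I error shows no inflation. Bias would need a non-random draw, which cannot be checked from the text.
- *The imbalance could be as large as a PRP effect.* At ICC 0.3 the SD of the woman-level part is about 10 points (√(0.25 × 0.3 × 27.04/196) = 10.2 in layout A). The illustrative effect is 40 points. Binomial noise from 14 per arm dominates.
- *Every woman could be her own control.* In layout B, 8 of 15 women have one oocyte.
- *A split would balance PRP storage age or batch.* PRP was "stored at -80°C until use", but the control arm receives none, so its age cannot differ between arms. The text describes one donor and one collection, and no batches. Only retrieval date can be balanced.

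Three further objections stand in part. The gain could be near zero, because the ICC is unknown. The power gain needs a change of test as well as of allocation. And the text is in the past tense, so for the present oocytes what remains is reporting. None of these removes the point: on the stated variance model, the split never increases the variance of the risk difference at any ICC of 0 or more.

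**Conclusion.** The concern holds as a loss of precision, not as a bias. Siblings must be present among the 28 and no split by woman or day is reported. If none was used, the variance of the risk difference is unchanged at ICC 0, about 3–10% larger at 0.1, 9–37% larger at 0.3 and 17–83% larger at 0.5 than with a within-woman split. These ranges rest on assumed ICCs, assumed oocytes per woman, 50% maturation and the stated 14 v 14. The gain in power appears only with a test that matches the allocation.

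The count is a separate open question that bears on this one. If pilot oocytes are inside the 28, they would not have been randomised with the rest, the calculations above would not describe the actual comparison, and that would be a more serious allocation problem than the missing split.

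**What to change.** For any allocation still to be made:

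1. On each retrieval day, number a woman's eligible oocytes in a fixed order and use a pre-generated list to send half to 0% and half to 5%.
2. Assign odd and single oocytes from a separate blocked list, so that the totals stay equal.
3. Replace the unstratified Fisher test with a re-randomisation test in the same strata (each woman, plus one joint stratum for odd and single oocytes), preferably with mid-p. Do not keep Fisher, and do not use a strictly within-woman exact test.

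If allocation is already complete, tabulate oocytes by woman, retrieval day and arm. State that the comparison was not balanced by woman, or state the restriction that was used. Apply steps 1–3 to further oocytes or a repeat experiment.

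In either case, reconcile the 28 with 34 − 9 = 25, and say whether any pilot oocyte was counted in the main comparison.

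The cost is a sentence on allocation, a sentence on the test and a per-woman list at the bench, with no extra oocytes, women or procedures. If the ICC is near zero, the price is up to about 1–2 points of mid-p power, or about 5 points without mid-p.

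### For the binary primary outcome the plan specifies only a Fisher p-value, with no effect measure or interval; Fisher is valid but conservative at 14 v 14, and the variance reason given for it does not apply.

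*Combined protocol and SAP*

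**What the plan says.** The opening methods text defines a yes/no endpoint per oocyte: "The primary outcome was oocyte maturation, defined by the transition from GV to MII stage", judged at 24 hours. On the design it says that "the remaining 28 GV-stage oocytes were randomly allocated into two groups", 14 to control and 14 to 5% PRP. The oocytes were "retrieved via the ovum pick-up (OPU) procedure from 15 women diagnosed with PCOS".

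The Statistical Analysis section then says: "Maturation outcomes were analyzed using Fisher's exact test in IBM SPSS Statistics version 25", with significance at p below 0.05. It adds that the method "was chosen due to the small sample size and comparable variance among groups". The total oocyte score is to be described only. No effect measure or confidence interval is named for maturation. The section does not state whether the test is one- or two-sided, and the documents give no sample-size or power calculation.

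**The concern.** There are three strands, in order of weight.

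- **No estimate.** A test and a threshold are the whole specification for the primary outcome. In a comparison of this size a non-significant result can coexist with a very large benefit. Only an interval shows this.
- **A conservative test.** With small equal arms Fisher's test can reject well below its nominal 5%. Another exact test may recover some power while still holding the error rate at 5%.
- **A reason that does not apply.** Fisher's test has no equal-variance condition. The variance of a yes/no outcome is p(1-p), so it is fixed by the rate. Rates of 40% and 80%, for example, give 0.24 and 0.16.

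At stake is what the trial can conclude about PRP, above all if the p-value is above 0.05.

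**Working it through.** The plan states no power, error rate or assumed maturation rates, so there is no figure of its own to reproduce.

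**Inputs from the documents:** 14 control and 14 treated oocytes; binary outcome; Fisher's test; threshold 0.05; 15 women.

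**Assumptions:** two-sided test, independent oocytes, and the maturation rates shown below.

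**1. What a p-value alone leaves open.** Take a hypothetical 7/14 (50.0%) v 10/14 (71.4%). Fisher p = 0.44. The Wilson limits for each arm are [p + z²/2n ± z√(p(1-p)/n + z²/4n²)] / (1 + z²/n), with z = 1.96:
- 7/14: 26.8% to 73.2%
- 10/14: 45.4% to 88.3%

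Newcombe's interval combines them around the difference of 21.4 points:
- lower: 21.4 - √((71.4-45.4)² + (73.2-50.0)²) = 21.4 - 34.9, about -13 points
- upper: 21.4 + √((88.3-71.4)² + (50.0-26.8)²) = 21.4 + 28.7, about +50 points

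**2. Actual size at 14 v 14.** There are 15 × 15 = 225 possible tables (a, b). Size at a common rate p is the sum of Bin(a; 14, p) × Bin(b; 14, p) over the tables with p-value below 0.05.
- Fisher: 0.4% at p = 0.1, 1.6% at 0.2, 2.1% at 0.3, 2.0% at 0.4, 1.7% at 0.5, and symmetric above 0.5. The maximum is 2.14%. Read as one-sided, the maximum is 2.08%.
- Boschloo (tables ordered by the two-sided Fisher p-value): maximum 4.16%. It keeps every Fisher rejection and rejects 14 more tables.

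**3. Power.** The same sum, with rates p1 and p2 in the two arms. The 12 v 13 columns are included because the counts conflict: three pilot groups of three use 9 oocytes, and 34 - 9 = 25, not 28.

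| Assumed rates, control v PRP | 14 v 14: Fisher | Boschloo | Gain (points) | 12 v 13: Fisher | Boschloo | Gain (points) |
|---|---|---|---|---|---|---|
| 30% v 70% | 39.9% | 53.0% | 13 | 51.2% | 51.7% | 0.5 |
| 40% v 80% | 44.3% | 54.4% | 10 | 53.1% | 54.9% | 2 |
| 50% v 80% | 26.0% | 33.4% | 7 | 32.5% | 35.9% | 3 |
| 50% v 90% | 53.6% | 63.2% | 10 | 57.7% | 64.8% | 7 |
| 30% v 80% | 64.6% | 75.5% | 11 | 73.6% | 74.2% | 1 |
| 40% v 90% | 74.2% | 80.7% | 7 | 77.3% | 81.0% | 4 |

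At 12 v 13 Fisher's maximum size is 4.3%. At 11 v 14 it is again 4.3%, and the gain at 30% v 70%, 40% v 80% and 50% v 90% ranges from about 2 to 16 points. The conservatism belongs to the particular split, not to Fisher's test in general.

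**4. One table where the tests disagree.** A hypothetical 5/14 v 11/14 gives Fisher p = 0.054 and Boschloo p = 0.028. The difference is 43 points, Newcombe 95% interval 6 to 67.

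**5. Oocytes from the same woman.** A simulation assumed 13 women with two oocytes and two with one (13 × 2 + 2 = 28), a common rate of 0.5 and an intraclass correlation of 0 to 0.5. If oocytes are randomised individually, Fisher's size stays at 1.8% to 1.9%. If each woman's oocytes stay together, it is about 3% at a correlation of 0.2 and about 5% at 0.5.

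**The case against.** Fisher's test is a standard and valid choice for a small 2×2 table, and small sample size is a proper reason for it. It controls the error rate, so preferring another exact test is partly a matter of taste. All of that stands, and it is why the choice of test is the lesser part of this point.

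A reader might infer several stronger claims that the documents do not support.

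- **That the true error rate is 2%.** This is an unconditional maximum at exactly 14 v 14. Conditional on the total number matured, the size ranges from 0 to 4.6%. At other splits of the available oocytes the maximum is about double.
- **That the test decides the conclusion.** At 14 v 14 the two tests differ in 14 of 225 tables. The chance of landing in one equals the power gain, 7% to 13% in the scenarios above. The rates are assumed, and the 5/14 v 11/14 example is chosen from those tables.
- **That no effect size was reported, or that a non-significant result was read as no effect.** The text is a methods account without results. It shows what was specified, not what was reported or found.
- **That Boschloo should now replace Fisher.** The analysis is described in the past tense. Changing to a more powerful test after seeing the data would be a post hoc choice.

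The missing effect measure and interval survive all of these objections, because that gap does not depend on the test, the split or the rates.

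**Conclusion.** The point holds in a limited form. No effect measure or confidence interval is specified for the primary outcome, and at about 14 per arm a non-significant p-value is compatible with differences as large as 50 points. The variance reason does not apply to Fisher's test.

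The power argument is secondary: about 7 to 13 points at 14 v 14 and about 0.5 to 7 points at 12 v 13. It rests on assumed maturation rates, a two-sided reading, independent oocytes and a split that the stated counts leave uncertain. The intervals shown also treat oocytes as independent, although they come from 15 women. This is a cheap improvement to precision and interpretation; it does not make the stated test invalid.

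**What to change.** - Make the risk difference in maturation, with a Newcombe or score 95% interval, the main result. Base any statement of no effect on that interval.
- Present it with an analysis that accounts for oocytes from the same woman.
- Keep Fisher as the stated test and state its sidedness. Add Boschloo as a labelled sensitivity analysis. Make Boschloo the primary test only if the results have not been seen.
- Delete the variance reason and keep small sample size.
- Reconcile 34 retrieved, 9 in the pilot and 28 randomised, and state the final numbers per arm.

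The cost is a few sentences and free software (Boschloo's test is in R and SciPy). The downside is one analysis outside the stated package.
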